The Effectiveness and Mechanism Study
of Auricular Needling in Treating
Cancer Induced Anorexia

Research programme

2016. 05. 01

Background of the study

Anorexia nervosa is a common clinical symptom in tumor patients. The incidence of anorexia ranges from 6% to 74% depending on the type of tumor and clinical stage. It is common in patients with gastrointestinal tumors and advanced tumors, and the incidence of anorexia in advanced patients receiving palliative care ranges from 25% to 45%, and in severe cases, it is accompanied by malnutrition, or even malignant fluid state. In some studies, anorexia is found in up to 80% of patients with advanced stage, among which gastric cancer patients account for about 60%. Once anorexia occurs in tumor patients, it not only affects the implementation of the treatment plan, increases the difficulty of treatment, and affects the quality of survival of patients, but also can lead to malignant tumor patients die of malnutrition and depletion, which affects the survival time of the patients, and becomes the direct cause of death of tumor patients. Therefore, an in-depth understanding of the characteristics of anorexia nervosa, associated factors, assessment tools and interventions is an important therapeutic need faced by patients with advanced tumors, and a key direction for oncology research. How to optimize the selection of interventions against anorexia nervosa and to explore its mechanism of action are also scientific problems that we TCM oncologists need to solve in clinical practice. At present, the treatment of anorexia nervosa includes medication, nutritional therapy and psychotherapy, etc., with different efficacy and outstanding problems. Among them, megestrol acetate, as a kind of progestin with anabolic effect, has the functions of promoting appetite, increasing body weight, and improving the quality of patient's survival, and it is the only approved drug for the treatment of anorexia nervosa with cancer, but the toxic side effects caused by it, such as stimulation of tumor growth, venous thrombosis, and water and sodium retention, should not be ignored. Chinese herbal medicine has some research results in the treatment targeting the improvement of appetite, but it is not well accepted abroad. Clinical significance is insufficient. By combining the study of ancient literature with modern research, our department has taken a new approach to propose a new idea of clinical treatment, intervening auricular acupuncture in the treatment of cancerous anorexia nervosa. In the preliminary clinical pre-test, the initial effect is satisfactory, auricular acupuncture treatment can significantly improve the patient's appetite, showing its simple, convenient, inexpensive, tested characteristics, safe and reliable, but the technology needs further verification, standardization and improvement. However, this technique needs to be further validated, standardized and improved. Auricular acupuncture, which is highly accepted in the West, lacks high-quality evidence-based clinical efficacy and mechanism studies, which affects the influence of auricular acupuncture and warrants in-depth research.

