
This research proposal is in response to the National Natural Science Foundation of China's top-level project (Project No. 81573958; Title:

Auricular Acupuncture for Clinically Advanced Tumor Patients' Appetite Intervention and Mechanism Research).

Research Objectives

To objectively evaluate the clinical efficacy of auricular acupuncture in improving the appetite of tumor patients, to verify and improve its technique, to determine the therapeutic points and treatment course, and to provide a strong evidence-based medical basis for auricular acupuncture intervention in tumor therapy. We will validate and improve its technique, determine the therapeutic points and treatment course, and provide a strong evidence-based

medical basis for the intervention of auricular acupuncture in the treatment of tumors.

Research content

1 Type of study design

This study used a randomized, parallel-controlled research method. Based on the principle of voluntary participation, baseline information was included and collected, random seeds were generated by the SAS 9.2 statistical software random seed generator, and in a ratio of 1:1, it was proposed to randomly assign 60 subjects meeting the inclusion criteria to the ear acupuncture group and the control group. Each group of 30 cases, statistical expert design, after the preparation of the randomization scheme, the control and implementation of the allocation by those who are not directly involved in the grouping.

2 Sample size setting

This study was an exploratory study, considering 30 cases in each group, totaling 60 patients.

3 Study population

Sixty patients with anorexia nervosa of malignant tumors of stage III and IV who attended outpatient clinics or were hospitalized in the Department of Oncology of Xiyuan Hospital of China Academy of Traditional Chinese Medicine from May 1, 2016 to October 31, 2017.

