### 2 Statistical analysis plan

Statistical analyses will be calculated using SAS 9.2 statistical analysis software.

The primary validity analysis dataset will be FAS, and PPS will also be analyzed.

All statistical tests will be two-sided, and a p-value of less than or equal to 0.05 will be considered a statistically

The differences tested were considered statistically significant.

Measures for each visit in the different treatment groups were described statistically as mean  $\pm$  standard deviation. Comparisons were made with the baseline values at the time of enrollment using the paired t-test. The paired t-test was used to compare pre- and post-treatment differences within groups. Changes before and after treatment in each group were compared using analysis of variance (ANOVA). The count data of each visit of different treatment groups were statistically described by frequency counts (constitutive ratio). Changes before and after treatment in each group were analyzed using the  $\chi^2$  test or nonparametric The  $\chi^2$  test or non-parametric test was used.

Shedding analysis: The  $\chi^2$  test will be used to compare the total shedding rate and the shedding due to adverse events in each group.

Balanced analysis of baseline values: ANOVA or  $\chi^2$  test will be used to compare demographic data and other baseline indicators to measure how well balanced the two groups are. measure how well the two groups are balanced.

Effectiveness analysis: PPS and FAS were used to analyze the primary and secondary indicators; since this study is a multicenter clinical trial, the impact of central effects on the efficacy indicators should be considered in the analysis. Since this study is a multicenter clinical trial, the influence of center effect on the efficacy indexes should be considered in the analysis.

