Safety analysis: the X test was used to compare the incidence of adverse events in the two groups, and the adverse events occurred in this trial were described in a list. Adverse events: the X test was used to compare the incidence of adverse events in the two groups, and the adverse events occurred in this trial were described in a list; the changes of normal/abnormal laboratory test results before and after the trial were analyzed, as well as the relationship between the abnormal changes and the test drug. Safety analysis: The X test was used to compare the incidence of adverse events in the two groups and to describe the adverse events in this trial.

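### Chi-square at 0.05 is the only between-arm inference planned for adverse events and dropout; at 30 per arm it says little, and no interval or risk difference is planned.

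*SAP*

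**What the plan says.** The Safety analysis paragraph of SAP section 2 states that the chi-square "test was used to compare the incidence of adverse events in the two groups". It adds that "the adverse events occurred in this trial were described in a list", and that laboratory shifts between normal and abnormal, and their relation to treatment, will be examined.

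For dropout, the Shedding analysis paragraph of the same section says that the chi-square "test will be used to compare the total shedding rate and the shedding due to adverse events in each group". The general rule there is "All statistical tests will be two-sided, and a p-value of less than or equal to 0.05 will be considered a statistically" significant result.

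Protocol sections 7.2 and 7.3 add severity grades, causality grades and an incidence. The incidence counts events graded definitely related, possibly related or undetermined, over evaluable patients. Protocol section 4.3.2 asks that reasons for withdrawal be recorded where possible.

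On size, Protocol section 2 (Sample size setting) says: "This study was an exploratory study, considering 30 cases in each group, totaling 60 patients". No event rate, dropout rate, power or safety margin is given. Neither document mentions, for safety or dropout, a confidence interval, a risk difference, an exact test or a rule for sparse tables.

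**The concern.** A test with low power gives the reader one of two words, significant or not, and at this size it will often give the second even when a real difference exists. What a reader of an exploratory trial needs is how frequent events could be, and how far apart the arms could be. The plan produces neither.

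Three features make this matter here.

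- Needle-site events, such as the skin irritation and local pain named in Protocol section 4.3.4, come from a device that the control arm does not receive. For these the control count is zero by design, so the comparison adds nothing. The useful quantity is the needling-arm incidence and its upper limit.
- The Background calls the technique "safe and reliable, but the technology needs further verification", so the safety results are likely to be cited.
- Missing primary data are filled by last observation carried forward (SAP section 1). How many patients leave each arm, when and why, is therefore information that a reader of the efficacy result will want. The SAP offers only a p-value on total dropout and on dropout due to adverse events.

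**Working it through.** **Inputs.** 30 per arm, 1:1 (Protocol sections 1 and 2); two-sided, significant if p ≤ 0.05 (SAP section 2). The SAP names no chi-square variant, so Pearson without correction, Yates and Fisher are shown. All event and dropout rates below are assumptions. The sample size has no calculation to reproduce beyond 30 + 30 = 60.

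**Three events against none.**

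- Pearson: 60 × (3×30 − 27×0)² / (30 × 30 × 3 × 57) = 486,000 / 153,900 = 3.158, p = 0.076.
- Yates: p = 0.236.
- Fisher: 2 × C(30,3) / C(60,3) = 2 × 4,060 / 34,220 = 0.237.
- Smallest expected count: 3 × 30 / 60 = 1.5, below the usual 5.

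**Dependence on the variant.**

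| Events (needling v control) | Pearson p | Yates p | Fisher p |
|---|---|---|---|
| 3 v 0 | 0.076 | 0.236 | 0.237 |
| 4 v 0 | 0.038 | 0.121 | 0.112 |
| 5 v 0 | 0.020 | 0.062 | 0.052 |
| 6 v 0 | 0.010 | 0.031 | 0.024 |

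At 4 v 0 and 5 v 0 the verdict turns on a choice that the SAP does not make.

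**What estimation would show.**

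- 3/30: 10.0%, Clopper-Pearson 95% interval 2.1% to 26.5%.
- Risk difference for 3 v 0, Newcombe. The Wilson limits are 3.5% to 25.6% for 3/30 and 0% to 11.4% for 0/30. Lower: 0.100 − √[(0.100 − 0.0346)² + 0.1135²] = −0.031. Upper: 0.100 + (0.2562 − 0.100) = 0.256. So +10.0 points, −3.1 to +25.6.
- 0/30: exact two-sided upper limit 1 − 0.025^(1/30) = 11.6%.
- 0 v 0: Newcombe interval −11.4 to +11.4 points.

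**Power at 30 per arm.** This sums the binomial probabilities of all tables with p ≤ 0.05.

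| Assumed true rates | Pearson | Fisher |
|---|---|---|
| Events 10% v 0% | 35% | 7% |
| Events 15% v 5% | 26% | 9% |
| Events 20% v 5% | 45% | 24% |
| Events 20% v 10% | 19% | 10% |
| Events 30% v 10% | 50% | 37% |
| Dropout 10% v 25% | 34% | 21% |

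Check of the first row: against zero control events, Pearson needs at least 4 needling events. P(X ≤ 3 | 30, 0.10) = 0.647, so power is 1 − 0.647 = 0.353. At 15% v 0%, P(X ≤ 3 | 30, 0.15) = 0.322, so a rate of that size would still be missed about one time in three.

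The safety set also requires a follow-up visit (SAP section 1), so either arm could fall below 30. These figures are then on the favourable side.

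**The case against.** The strongest reply is that the plan does more than test. It has severity and causality grading, a defined incidence, an event listing and laboratory changes. That is right: a reader who inferred that safety is judged solely by a p-value would be overstating the case. For dropout, the p-value is the only analysis in the SAP, though the Protocol does ask for reasons to be documented.

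A reader might also infer that the sponsor intends to conclude safety, or balanced dropout, from p > 0.05. No section says so; there is no safety hypothesis, margin or decision rule, and the stated objectives concern efficacy, points and course of treatment. The Background's remark about safety describes a pre-test, and the verification it asks for is of the technique in general. Nor does the dropout test clear the efficacy result: the full analysis set with carried-forward values is primary whatever that test shows.

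Finally, low power for adverse events is normal in a declared exploratory trial of 60, and anyone with the counts could compute the intervals. This stands as a limit on severity. It does not defend the test, because an exploratory study is the setting in which estimates serve better than significance verdicts, and prespecifying them costs almost nothing.

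**Conclusion.** The point holds as a weak analysis choice. Chi-square at 0.05 is the only between-arm inference for adverse events and dropout, unaccompanied by any interval or risk difference, with the variant unnamed for tables likely to be sparse. In the scenarios tabulated, power is 50% or less under Pearson and 37% or less under Fisher. A needling arm with no events would leave rates of up to 11.6% open.

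The power figures rest on assumed rates, since the documents give none, and on 30 evaluable patients per arm. The p-values and intervals depend only on the illustrated counts and that denominator. No false conclusion is stated in the plan, and the change proposed is an inexpensive improvement.

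**What to change.** Make estimation the basis of safety and dropout reporting in SAP section 2:

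- Patients with at least one adverse event, by arm, with Clopper-Pearson 95% intervals and the risk difference with a Newcombe 95% interval. Give this alongside the causality-based incidence of Protocol section 7.3.
- Needle-site events as needling-arm incidence with its exact interval, without a control comparison.
- Dropout by arm, reason and visit, with the risk difference and its interval.
- A control-arm definition for the safety set. SAP section 1 requires use of a study drug, which the control arm does not receive, so as written the risk difference has no clear control denominator. The causality grading behind the Protocol incidence also refers to a drug, so say how control events are counted.
- If a p-value is kept, name the variant and treat it as descriptive. State that p > 0.05 is not evidence of safety or of balanced dropout.

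The cost is SAP wording and standard SAS output on data already collected. The downside is that intervals at 30 per arm are wide, so the safety statement becomes less favourable.

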3.1.2.2 Non-Spleen (Stomach) Deficiency Symptoms

Any other syndrome that does not meet the diagnostic criteria of Spleen (Stomach) Deficiency.

4 Selection and Withdrawal of Subjects

4.1 Inclusion criteria:

- ① Patients with malignant tumors diagnosed pathologically/cytologically and with stage III or IV disease;
- ① Patients with malignant tumors diagnosed by pathology/cytology, with stage III or IV disease;
- ① Patients with malignant tumors diagnosed by pathology/cytology, with disease stage III and IV;
- ③ Age 18 ~ 80 years old, gender is not limited; ④ KPS score ≥ 60 points;
- ⑤ The estimated survival period is more than 3 months;
- ⑥ Patients who voluntarily accept the treatment of this trial, with informed consent and good compliance.

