4.2 Exclusion Criteria

- ① Those who do not meet the inclusion criteria;
- ① Those who do not meet the inclusion criteria; ② Those who have abnormalities in blood routine, liver and kidney function indexes more than twice;
- Those with obvious eating disorders, gastrointestinal obstruction symptoms, heart disease and poor control of diabetes mellitus;
- ③ Those with obvious eating disorders, gastric obstruction symptoms, poor control of heart disease and diabetes mellitus;
- ⑤ Participating in other clinical studies;
- ⑤ Participants in other clinical studies; ⑥ Pregnant women, lactating women, psychiatric patients.

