5.2 Treatment program

5.2.1 Ear acupuncture group

Ear acupuncture treatment + conventional nutritional support and symptomatic treatment (refer to "Diagnostic and therapeutic path of anorexia nervosa" of tumor nutrition and supportive therapy committee of China Anti-Cancer Association).

Commonly used main points: Shenmen, stomach, spleen, subcortex.

Auxiliary points: Sanjiao, sympathetic, liver, small intestine.

Methods: Embed an earring needle and fix it with adhesive tape, press each point for about 2 minutes each time, 2-3 times a day, the pressure depends on the tolerance of the individual, alternating between the two ears, 2-3 times a week, 4 weeks of treatment, observation until 8 weeks.

5.2.2 Control group: Conventional nutritional support and symptomatic treatment.

During the treatment period, both groups can use supportive therapy reciprocally, if there are treatment-related adverse events, they should be handled separately, and the causes, history, symptoms and treatment measures should be recorded in detail. During the treatment period, both groups of cases could adopt the international standard protocol (Version 3.2014 NCCN) with or without standard chemotherapy or or without standard chemotherapy or radiation therapy.

6 Observation Indicators

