6.5 Provisions on the time point of follow-up

6.5.1 Data collection before enrollment

Medical record collection: fill in the baseline data according to the requirements of the CRF form;

Chinese medicine evidence: identify according to the Chinese medicine identification criteria and check the box on the CRF table;

Vital signs, physical examination;

blood, urine, stool routine, liver function, kidney function (within 2 weeks before enrollment);

Imaging examination: chest radiograph or chest CT, abdominal B ultrasound or abdominal or pelvic CT (within 1 month before enrollment).

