6.5.2 Data collection at 2 weeks and 4 weeks of enrollment

Medical record collection: symptom-based anorexia assessment form, simplified appetite scale, fatigue symptom scale, appetite level, body weight, and Kahn's score according to the CRF form.

Therapeutic use of medications

TCM evidence: identify according to TCM identification criteria, check on the CRF form;

Vital signs, physical examination;

blood, urine, stool routine, liver function, kidney function (within 2 weeks);

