7.4 Handling of adverse events

- Reporting method

Any adverse events, such as patients' subjective discomfort and abnormal laboratory tests, should be taken seriously and analyzed carefully. Any adverse events, such as subjective discomfort of the patient and abnormal laboratory tests, should be taken seriously, analyzed carefully, and immediate measures should be taken to protect the safety of the subjects.

- Handling procedure

Record in detail in CRF, and record its persistence, regression and disappearance as appropriate.

- Handling of serious adverse events

If any serious adverse event occurs, the investigator should not only give prompt treatment on site, but also report to the clinical trial unit in charge and the investigator within 24 hours. Within 24 hours, the investigator should report to the unit in charge of the clinical trial and the monitor of the clinical trial; and within 24 hours, the investigator should report in writing to the State Food and Drug Administration (SFDA). Within 24 hours, the investigator shall report in writing to the State Food and Drug Administration on the occurrence of the adverse event and its handling.

Treatment: When a patient has an emergency situation, the principal investigator of the study unit will do the appropriate treatment according to the drug and the symptoms presented, notify the clinical supervisor of the results of the treatment, and the investigator should record the treatment in detail, the results, and sign on the case report form.

- Follow-up of unrelieved adverse events

All adverse events should be followed up until properly resolved or stabilized. All adverse events with predominantly test values should be followed up with laboratory results until normal

8 Data management

The investigator loaded the data into the case report form in a timely, complete, correct, and legible manner based on the subjects' original observation records.

Supervisors monitored that the study was conducted in accordance with the study protocol. Confirm that all case report forms were completed correctly and consistent with the original data. In case of errors and omissions, the researcher was asked to make corrections in a timely manner. Corrections should be made in such a way that the original record is legible and the corrections should be signed and dated by the investigator.

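### The named laboratory safety analysis has only two states, normal and abnormal, so worsening from an abnormal entry value is tabulated as no change

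*SAP*

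**What the plan says.** **Analysis.** In SAP section 2, the safety analysis states that "the changes of normal/abnormal laboratory test results before and after the trial were analyzed". The only addition is that abnormal changes are to be examined for a link with the study treatment. It gives no toxicity grade, no category by multiple of a reference limit and no worst-value rule. It also does not say which post-baseline visit is the comparison point.

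**Entry.** Protocol 4.2 excludes "Those who have abnormalities in blood routine, liver and kidney function indexes more than twice". No reference limit is attached to that threshold. The population in Protocol 4.1 is "Patients with malignant tumors diagnosed pathologically/cytologically and with stage III or IV disease". Protocol 5.2 adds that "During the treatment period, both groups of cases could adopt the international standard protocol", with or without chemotherapy or radiation therapy.

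**Data.** Blood, urine and stool routine, liver function and kidney function are scheduled before enrolment and at weeks 2, 4 and 8 (Protocol 6.5.1 to 6.5.3).

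**Follow-up.** Protocol 7.4 first has every adverse event followed to resolution or stability. It then says: "All adverse events with predominantly test values should be followed up with laboratory results until normal".

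**The concern.** A before/after table with two states measures crossings of a limit. It does not measure how far a value moves. That is tolerable when nearly everyone starts inside the normal range. Here the entry criteria let in patients who do not, and advanced cancer with chemotherapy allowed makes abnormal entry values plausible.

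Two errors follow, in opposite directions. Real worsening in a patient already abnormal is tabulated as stability, and a negligible movement across the limit is tabulated as deterioration. At stake is whether the one analysis named for laboratory data describes laboratory change in both arms fairly. The efficacy results are not affected.

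**Working it through.** The plan states no figure to reproduce for this point: Protocol section 2 sets 30 per group, 60 in total, as an exploratory size without a rate or a power. The check is first logical, then illustrative.

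**Step 1: can patients enter abnormal?** The exclusion threshold can be read in two ways.
- As a multiple of the normal limit: a value between 1 and 2 times the limit is allowed.
- As a number of occasions: one or two abnormal results are allowed.

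Under both readings the answer is yes.

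**Step 2: classify example pairs.** Values are multiples of an upper limit; a value is N if at or below 1 and A if above 1.

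| Baseline | Follow-up | Table entry | Counted as |
|---|---|---|---|
| 0.98 | 1.02 | N to A | deterioration |
| 0.9 | 1.5 | N to A | deterioration |
| 1.5 | 6 | A to A | no change |
| 1.8 | 5 | A to A | no change |

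This follows from the table's structure and needs no assumed rate.

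**Step 3: how many patients could show a new abnormality?** Let p be the share abnormal at entry on a given test. The number per arm is 30 × (1 − p). The documents do not give p. For an assumed p of 0.30 it is 30 × 0.70 = 21; for 0.60 it is 30 × 0.40 = 12.

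**Step 4: illustration of the loss.** Assume true worsening in 30% of one arm and 5% of the other, independent of entry status. Neither rate comes from the documents. If only N-to-A changes count, the counted rates are 0.30(1 − p) and 0.05(1 − p), and the expected count in the higher-rate arm is 30 × 0.30 × (1 − p). Power is the normal approximation for two proportions, two-sided 0.05: Φ[(d − 1.96·SE₀)/SE₁], where d is the difference in counted rates, SE₀ the pooled and SE₁ the unpooled standard error.

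| p | Able to show N to A, per arm | Expected counted, higher-rate arm | Power |
|---|---|---|---|
| 0 | 30 | 9.0 | 0.73 |
| 0.10 | 27 | 8.1 | 0.68 |
| 0.20 | 24 | 7.2 | 0.61 |
| 0.40 | 18 | 5.4 | 0.47 |
| 0.60 | 12 | 3.6 | 0.33 |

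The lower-rate arm expects only 30 × 0.05 = 1.5 patients even at p = 0, so the approximation is rough. The table shows the direction of the loss, not a forecast for this trial.

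**Step 5: is the worsening caught elsewhere?**
- *Adverse events.* Protocol 7.4 names abnormal laboratory tests as adverse events, and the SAP lists events and compares their incidence. No rule says when worsening of an already abnormal value becomes an event. Severity in Protocol 7.2 is judged by daily activities, so a large rise without symptoms could be rated mild. The incidence in Protocol 7.3 counts only the three causality classes from definitely related to undetermined.
- *Group means.* SAP section 2 describes measures at each visit by mean and standard deviation, with paired tests against baseline. It does not name laboratory values, and a mean over 30 patients dilutes a large change in a few.

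Both routes are possible; neither is defined for this case.

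**The case against.** The strongest reply is that the safety analysis is more than this one table. A marked rise can be recorded and listed as an adverse event, and the general rule for measures is not confined to efficacy. That stands. A reader might infer that the plan cannot detect laboratory deterioration at all; the documents do not support this. The blind spot belongs to the named table. The remaining gap is the missing rule for worsening from an abnormal baseline.

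A reader might also infer that the protocol sets a two-fold limit on which graded categories could be built. The wording is unclear and gives no reference limit. A two-fold category has no clear meaning for low blood counts, and the criterion does not cover urine or stool tests. Abnormal entry survives either reading; a scheme built on two-fold levels does not.

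Further, this is an exploratory trial of ear needling. The local effects named as grounds for withdrawal are skin irritation and pain, and no conclusion of laboratory safety is announced. This limits the weight of the point. It does not remove it, because four rounds of tests are scheduled and the SAP plans to analyse laboratory results for safety.

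Finally, the two follow-up sentences in Protocol 7.4 can be read as a general rule and a stricter specific one. That is fair, but for a patient who entered abnormal they can lead to different end points, since a return to the entry value need not be normal.

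**Conclusion.** The point holds for the laboratory analysis that the SAP names. In that table, every patient abnormal at entry on a test contributes nothing to the detection of worsening on it, and trivial crossings of the limit count as change. This rests only on the two-state definition and on entry criteria that admit some abnormality.

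The size is unknown, because the documents give no share abnormal at entry; the 12 to 21 of 30 and the power figures depend on assumed rates. It is an inexpensive improvement worth making, not a fault that undermines the trial. The follow-up wording in Protocol 7.4 is a separate, minor matter.

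**What to change.** In the SAP safety analysis:

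1. For blood routine, liver and kidney tests, replace the normal/abnormal comparison with a descriptive shift table by arm, from baseline to the worst post-baseline value over weeks 2, 4 and 8. Use a standard published toxicity grading, named with its version, with low and high directions shown separately.
2. Report by arm the number and proportion of patients who worsen by at least one grade.
3. Keep normal/abnormal for urine and stool routine.
4. State when worsening from an abnormal baseline is recorded as an adverse event.
5. Confirm that the case report form stores numerical values and reference ranges. The form is not among the documents, so this cannot be taken for granted.

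Separately, the sponsor should reconcile the two follow-up sentences in Protocol 7.4 for patients who entered with abnormal values.

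The cost is SAP wording and a longer table; no tests are added. With 30 per arm many cells will be sparse, so the table should stay descriptive and should not be used to claim absence of laboratory harm.
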